
For both IR and XR formulations, dose reductions may be made at any time for safety/tolerability reasons. Incremental dose increases will also be allowed during the Treatment Period (Table 1 and Table 2) at the discretion of the Investigator (as clinically indicated) and according to the stepwise titration scheme outlined in Table 4.

Subjects will be assessed for clinical worsening during each clinic visit. If clinical worsening is confirmed, the Investigator may opt to either continue treatment with ralinepag at the current dose, increase the dose of ralinepag, interrupt treatment, or discontinue the subject at his/her discretion. Addition/dose increases/substitutions of 1 drug within the ERA class and 1 within the PDE5-I/soluble guanylate cyclase (sGC) stimulator class are also permissible.

In addition, all subjects will be contacted at the time of Study APD811-007 closure to assess vital (mortality) status. The vital status follow-up contact of subjects will depend on local regulations or specific agreement with the subject and Investigator.

Upon termination of the study, subjects will complete an End of Study Visit. A 28-day Follow-up Visit will be conducted to ensure appropriate subject safety. This visit may be conducted by telephone or in person based upon the Investigator's discretion. Subjects who remain on ralinepag at study termination and meet all eligibility criteria are eligible to roll into the open-label extension study (ROR-PH-303).

Concomitant Medications:

Subjects are permitted oral disease-specific PAH therapy consisting of an ERA and/or a PDE5-I or sGC stimulator, but not both. The on-study addition/substitution of an ERA, PDE5-I/sGC stimulator, if on a single such agent at Baseline, or dosage increase for such agents is permitted. In addition to ralinepag, subjects can be prescribed no more than 1 agent from the ERA class and 1 from the PDE5-I/sGC stimulator class at any 1 time. Substitution and dose adjustment within each of these classes is permitted. Subjects should be evaluated for the presence of clinical worsening if additional therapy or dose adjustments/substitutions of current therapies are required.

In addition, the following therapies, which may affect PAH, are permitted and may be adjusted in dose as needed:

- Vasodilators (including calcium channel blockers)
- Digoxin
- Spironolactone
- L-Arginine supplementation

Diuretics may be dosed as clinically indicated throughout the study.

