^c This visit may be conducted by telephone or in person based upon the Investigator’s discretion.

^d Safety ECGs should be completed pre-dose. After the last subject enrolled in Study APD811-007 completes approximately 6 months of treatment and a cumulative all-subject data analysis is performed, as outlined in Section 9 (Planned Statistical Methods), ECGs will subsequently be conducted locally at the discretion of the

- Investigator (as clinically indicated) during the Q3 monthly visits. The ECG will be performed at the End of Study Visit. Locally collected ECG values for RR, PR, QRS, QT, QTc, QTcB, and QTcF will be collected in the Sponsor's clinical database.
- ^e Clinical laboratory tests will include hematology, serum chemistry, coagulation, and urinalysis. Clinical laboratory tests will be completed pre-dose. After the last subject enrolled in Study APD811-007 completes approximately 6 months of treatment and a cumulative all-subject data analysis is performed, as outlined in Section 9, clinical laboratory tests will subsequently be conducted locally at the discretion of the Investigator (as clinically indicated) during the Q3 monthly visits. A complete clinical laboratory test will be conducted locally at the End of Study Visit. Locally collected laboratory values that are abnormal and clinically significant will be collected in the Sponsor's clinical database along with the reference ranges.
 - ^f Serum hCG pregnancy tests will be completed pre-dose at each visit during the Treatment Period. After the last subject enrolled in Study APD811-007 completes approximately 6 months of treatment and a cumulative all-subject data analysis is performed, as outlined in Section 9, pregnancy testing (either serum or urine) will subsequently be conducted locally during each Q3 monthly and the End of Study Visit. Locally collected positive values for hCG will be collected in the Sponsor's clinical database along with the reference range.
 - ^g Vital sign measurements (blood pressure, heart rate, respirations, and body temperature taken in supine position after 5 minutes of rest) will be taken pre-dose.
 - ^h Subjects treated with ralinepag in Study APD811-003 study will continue on current dose.
 - ⁱ WHO/NYHA Functional Class will be assessed pre-dose at all visits.
 - ^j An assessment for further dose escalation or de-escalation will be conducted during the Q3 months.

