Abbreviations: 6MWT, 6-Minute Walk Test; BNP, brain natriuretic peptide; ECG, electrocardiogram; hCG, human chorionic gonadotropin; MTD, maximum tolerated dose; NT-proBNP, N-terminal pro-brain natriuretic peptide; NYHA, New York Heart Association; Q3, every 3; QTcB, QT interval corrected for Bazett’s formula; QTcF, QT interval corrected for Fridericia’s formula; RHC, right heart catheterization; RR, respiratory rate; WHO, World Health Organization

^a Reference to pre-dose and post-dose activities in this schedule apply to the morning dose of study drug. Study drug should be taken with food.

^b The Week 25 Visit from Study APD811-003 will serve as the Baseline/Day 1 Visit for Study APD811-007.

- ^c This visit may be conducted by telephone or in person based upon the Investigator's discretion.
- ^d Safety ECG measurements to be completed at Baseline and at Weeks 1 to 9, unless the subject reaches a stable MTD and the subject transitions into the Treatment Period; ECGs will be completed pre-dose and 2 hours post-dose. After the last subject enrolled in Study APD811-007 completes approximately 6 months of treatment and a cumulative all-subject data analysis is performed, as outlined in Section 9, ECGs will subsequently be conducted locally at the discretion of the Investigator (as clinically indicated) during the Q3 monthly visits. The ECG will be performed at the End of Study Visit. Locally collected ECG values for RR, PR, QRS, QT, QTc, QTcB, and QTcF will be collected in the Sponsor's clinical database.
- ^e Clinical laboratory tests will include hematology, serum chemistry, coagulation, and urinalysis. Clinical laboratory tests will be completed pre-dose. After the last subject enrolled in Study APD811-007 completes approximately 6 months of treatment and a cumulative all-subject data analysis is performed, as outlined in Section 9, clinical laboratory tests will subsequently be conducted locally at the discretion of the Investigator (as clinically indicated) during the Q3 monthly visits. A complete clinical laboratory test will be conducted locally at the End of Study Visit. Locally collected laboratory values that are abnormal and clinically significant will be collected in the Sponsor's clinical database along with the reference ranges.

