- ^f Serum pregnancy test will be completed pre-dose at each visit during the Treatment Period. After the last subject enrolled in Study APD811-007 completes approximately 6 months of treatment and a cumulative all-subject data analysis is performed, as outlined in Section 9 (Planned Statistical Methods), pregnancy testing (either serum or urine) will subsequently be conducted locally during each Q3 monthly and the End of Study Visit. Locally collected positive values for hCG will be collected in the Sponsor's clinical database along with the reference range.
- ^g Vital sign measurements (blood pressure, heart rate, respirations, body temperature, and pulse oximetry [SpO₂]), taken in supine position after 5 minutes of rest) will be taken at pre-dose on Day 1, and pre-dose on the first day of each dose increase. On the first day of each dose increase, blood pressure and heart rate will be taken approximately every hour for the first 4 hours after study drug administration. Vital signs will be measured prior to any blood draw that occurs at the same time point.
- ^h The 6MWT should be completed pre-dose at approximately the same time of day at each designated visit.
- ⁱ WHO/NYHA Functional Class will be assessed pre-dose at all visits.
- ^j An assessment for further dose escalation or de-escalation will be conducted during the Q3 months.
- ^k After the last subject enrolled in Study APD811-007 completes approximately 6 months of treatment and a cumulative all-subject data analysis is performed, as outlined in Section 9, pro-BNP and NT-proBNP testing will subsequently be conducted locally at the discretion of the Investigator (as clinically indicated) during the Q3 monthly visits. Locally collected values will be entered into the Sponsor's clinical database along with the reference ranges.
- ^l At 1 year (± 3 months) after the subject enrolls into Study APD811-007, an RHC assessment will be conducted. If the subject has been in Study APD811-007 beyond 1 year (± 3 months) at the time of regulatory/ethics approval of Amendment 2, an RHC assessment will be conducted at 2 years (± 3 months) instead. If a subject has been enrolled in Study APD811-007 more than 2 years at the time of regulatory/ethics approval of Amendment 2, an RHC will be performed at the time of those approvals.

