6.5.3 ECG Assessment

Baseline ECGs will be compared with the final ECG.

The Investigator will be responsible for the review and interpretation of safety ECGs on site and determining if the ECG is normal, abnormal clinically insignificant, or abnormal clinically significant. Findings will be documented in the Case Report Form (CRF). This information will be used in the ongoing safety review during the conduct of the study.

6.6 6-MINUTE WALK TEST

The 6-Minute Walk Test (6MWT) should be conducted according to the guidelines in Appendix 1, which have been adapted from the guidelines issued by the American Thoracic Society, *ATS Statement: Guidelines for the Six-minute Walk Test*.¹⁶ Technicians performing the test will be trained according to published procedures (Appendix 1). Tests will be performed at approximately the same time of day for each test in order to minimize intra-day variability. The 6MWT performed at the Week 25 Visit of Study APD811-003 will serve as the Baseline assessment for Study APD811-007.

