6.8 RIGHT HEART CATHETERIZATION

At 1 year (± 3 months) after the subject enrolls into APD811-007, an RHC assessment will be conducted. If the subject has been in the APD811-007 study beyond 1 year (± 3 months) at the time of regulatory/ethics approval of Amendment 2, an RHC assessment will be conducted at 2 years (± 3 months) instead. If a subject has been enrolled in APD811-007 for more than 2 years at the time of regulatory/ethics approval of Amendment 2, an RHC will be performed at the time of those approvals. It is recommended that every effort should be made to take the measurements approximately 4 hours after the last dose of study drug. An RHC should be performed when a subject terminates from the study early if an RHC has not been conducted within the previous year.

The following values will be obtained and recorded: PAP (systolic, diastolic, and mean), heart rate, right atrial pressure, PCWP right ventricular pressure and cardiac output, PVR, arterial and mixed venous oxygen saturation (if applicable). Systemic vascular resistance (SVR) will be estimated from BP measurements. Further specifications will be provided in a separate study manual.

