6.11 BNP/NT-PROBNP

As mean PAP increases, so does the brain natriuretic peptide (BNP)/N-terminal pro-brain natriuretic peptide (NT-proBNP) level as long as ventricular function is intact. In idiopathic PAH, the BNP/NT-proBNP level is related to functional impairment.

As BNP/NT-proBNP may be affected by recent exercise, subjects must be allowed to rest for a minimum period of **1 hour** following arrival at the clinic, prior to obtaining this blood sample. Similarly, this sample must be taken prior to the 6MWT. This sample should be taken with the subject in the same position at all appropriate visits, eg, sitting or semi-recumbent. Detailed instructions about sample collection will be provided in a separate sample collection manual.

After the last subject enrolled in APD811-007 completes approximately 6 months of treatment and a cumulative all-subject data analysis is performed, as outlined in Section 9, pro-BNP and NT-proBNP testing will subsequently be conducted locally at the discretion of the Investigator (as clinically indicated) during the Q3 monthly visits. Locally collected values will be entered into the Sponsor's clinical database along with the reference ranges.

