4. Two small cones to mark the turnaround points.
5. A chair that can be easily moved along the walking course.
6. Worksheets.
7. A source of oxygen.
8. Telephone.
9. Automated electronic defibrillator.

Subject Preparation

1. Comfortable clothing should be worn.
2. Appropriate shoes for walking should be worn preferably the same pair for each test.
3. A subject should use his or her usual walking aids during the test (cane, walker, etc).
4. The subject's usual medical regimen should be continued and study drug taken in the morning before the commencement of the 6MWT.
5. A light meal is acceptable before early morning or early afternoon tests.
6. Subjects should not have exercised vigorously within 2 hours of beginning the test.

Measurements

1. Repeat testing should be performed about the same time of day to minimize intra-day variability.
2. A "warm-up" period before the test should not be performed.
3. The subject should sit at rest in a chair, located near the starting position, for at least 10 minutes before the test starts. During this time, check for contraindications and make sure that clothing and shoes are appropriate. Record all pertinent information surrounding the test (ie, starting location, length of hallway, direction the subject will be walking, time of test, subject's general condition/feeling on the day of the test, and any other physical or medical information that may potentially influence the results of the test).
4. Subjects who require supplemental oxygen must breathe a stable oxygen dose for at least 15 minutes prior to the measurement of SpO₂ and until the end of the 6MWT (see below for SpO₂ requirements). It is critical that if oxygen was utilized during the screening 6MWTs, that it be utilized during all subsequent on-study tests and that it is

delivered in the same manner with the same flow. Note whether the oximeter signal quality is acceptable.

5. Set the lap counter to 0 and the time to 6 minutes. Assemble all necessary equipment (lap counter, timer, worksheets, etc.) and move to the starting point.
6. Instruct the subject as follows:

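### The protocol gives opposed rules for whether the 6-minute walk comes before or after the morning dose, and no planned 6MWD summary takes dose timing into account

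*Protocol*

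**What the plan says.** Table 2 is the schedule for subjects who received placebo in the parent study. Its footnote h reads "The 6MWT should be completed pre-dose at approximately the same time of day at each designated visit", and its footnote a fixes the meaning: "Reference to pre-dose and post-dose activities in this schedule apply to the morning dose of study drug".

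Protocol Section 6.6 makes no distinction by parent group. It says the test "should be conducted according to the guidelines in Appendix 1". In Appendix 1, Subject Preparation item 4 asks for the usual medical regimen to continue and for "study drug taken in the morning before the commencement of the 6MWT".

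Table 1, for subjects who received ralinepag in the parent study, labels several procedures as pre-dose (for example "Safety ECGs should be completed pre-dose") but attaches no timing note to the 6MWT.

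SAP 10.2 lists the last dose date and time and the hours from that dose to the walk. Its summaries give 6MWD and change from baseline by parent group and visit, without using either variable.

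**The concern.** For a former placebo subject on a dosing day, the two instructions cannot both be met. A site reading Table 2 would test before the morning dose, and a site reading Section 6.6 and Appendix 1 would test after it. Even if each site followed its own schedule table, former placebo subjects would be walked before the dose and former ralinepag subjects after it.

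The quantity at stake is the by-visit 6MWD summary. Part of a change from baseline, or of a difference between the two parent-group columns, could reflect where in the dosing interval the walk took place. 6MWD also enters one clinical worsening criterion, through a fall of at least 20%.

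**Working it through.** The documents give no figure to reproduce. The check compares the passages and asks whether any of them resolves the conflict.

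1. **Same dose, same test.** Footnote a ties pre-dose to the morning dose. Appendix 1 item 4 also concerns the morning dose, and it names study drug separately from the usual regimen, so it is not only about background therapy. The rules are opposed.

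2. **Precedence.** Section 6.6 applies Appendix 1 without exception. Table 2 does not say it overrides the appendix. Both are current text.

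3. **Visit list in Section 7.2.3.1.** It names dosing before the 6MWT, which might suggest an order. But it names BNP/NT-proBNP after the 6MWT, while Section 6.11 says "this sample must be taken prior to the 6MWT". The list is not a sequence and settles nothing.

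4. **Same time of day.** Section 6.6, footnote h and Appendix 1 all ask for this. It fixes clock time, not position relative to the dose. If a site keeps to one rule, timing within a subject should be stable, so mixing is mainly between sites.

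5. **Baseline.** The former placebo group's baseline walk precedes any ralinepag in this study, so the conflict affects only their post-baseline walks. For former ralinepag subjects the baseline is the parent study's Week 25 walk. The documents do not show whether its dose time is available.

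6. **Comparison with another measure.** For right heart catheterization, Section 6.8 recommends an effort to "take the measurements approximately 4 hours after the last dose of study drug". This is a recommendation only, but it shows that time since dose was considered for another efficacy measure.

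7. **Walks that fit neither rule.** After clinical worsening the investigator may "increase the dose of ralinepag, interrupt treatment, or discontinue the subject at his/her discretion". Table 5 includes every-other-day dosing, and Section 6.14.1 asks for End of Study procedures after premature discontinuation. Some walks will fall off drug or on a non-dosing day.

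Side note on exposure, for immediate-release capsules only. Protocol Section 1.1.3 gives a fed time to peak of about 4 h (one 30 mcg single-dose study) and a half-life of 20.5 to 26.4 h. Assume simple exponential decline from peak to the next dose:

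- Twice daily (12 h interval): 2^((12−4)/20.5) = 1.31 and 2^((12−4)/26.4) = 1.23.
- Once daily (24 h interval): 2^((24−4)/20.5) = 1.97 and 2^((24−4)/26.4) = 1.69. In Section 5.6.1.1 this regimen is only the step-down when 10 mcg twice daily is not tolerated.

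These are peak to pre-dose concentration ratios. They depend on the model and are not upper bounds. Appendix 1 sets no interval after the dose, so a walk need not fall at the peak. Section 1.1.3 also says the extended-release tablet reduces peak-to-trough fluctuation relative to the capsule for once-daily dosing. That comparison does not cover twice-daily capsules, so no extended-release figure is given. Nothing in the documents converts concentration into metres.

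**The case against.** The strongest reply is that this matters little. Efficacy is secondary under Protocol Section 9.2.2, SAP 10.2 plans only descriptive statistics for 6MWD, and safety is the primary analysis. The same-time-of-day rule limits variation within a subject. The SAP already lists hours from last dose, allows exploratory subgroups (Section 8.1) and permits unplanned analyses (Preface), so mixed timing would be visible to anyone who looked. The study is being discontinued (SAP Section 3), so new protocol wording can change few future walks.

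Most of this stands, and it sets the weight. It does not remove the contradiction. A listing also does not tell the reader of the 6MWD table whether its columns are comparable in timing. SAP Section 12 does not mention the conflict, but that section records changes to planned analyses and data not collected, so its silence is not a separate defect.

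A reader might infer that sites did mix timings and that the 6MWD results are biased. The documents do not show which rule was followed, and they support only that timings can differ. A reader might also infer that clinical worsening is distorted. Protocol Section 6.9 requires the 20% fall to be confirmed on two walks on different days and to occur together with worse functional class and right heart failure signs, so any effect there is likely small.

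**Conclusion.** The inconsistency is certain; its consequence is minor. Post-baseline 6MWD can mix dose timings between sites within the former placebo group, and timing can differ between the two parent groups shown side by side. Mixing within one subject is less likely. The primary safety objective is not affected.

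The size in metres cannot be computed, because the documents give neither a link between concentration and distance nor the share of walks done under each rule. The concentration ratios should not be read as an effect on 6MWD. The conclusion assumes only that Table 2 with its footnotes and Section 6.6 with Appendix 1 are both in force, as the current text has them.

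**What to change.** - **Protocol.** Reconcile Table 1, Table 2 footnote h, Section 6.6 and Appendix 1 to one timing rule for both groups. This review takes no position on which. Because the study is ending, the analysis and reporting steps carry most of the value.
- **Study report.** State which rule sites followed. If the dose time for the baseline walk of former ralinepag subjects is not available from the parent study, say that it is unknown.
- **SAP 10.2, one table.** Describe hours from last ralinepag dose to the 6MWT by parent group and visit.
- **SAP 10.2, one sensitivity summary.** Show 6MWD change from baseline by parent group, split by whether the morning dose on the day of the walk had been taken before it (yes or no). Show walks off drug or on a non-dosing day separately. Do not split further by formulation.

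The cost is one derived variable, one table, one summary and a sentence or two in the report. The post-baseline dose times are already in the planned listing. With approximately 60 subjects some cells will be small, and timing may track site, so the summary should be read as descriptive only.

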4 STUDY POPULATION SELECTION

4.1 STUDY POPULATION

The study population will include subjects with WHO Group 1 PAH who have completed Study APD811-003 or who were assigned to placebo and discontinued for clinical worsening and who are deemed appropriate candidates for participation in this long-term extension study.

All women, regardless of childbearing potential, must have a negative serum human chorionic gonadotropin (hCG) pregnancy test at each visit during the Treatment Period and at Week 5 of the Dose Titration Period, if applicable. Males and females of childbearing potential must use adequate means of contraception and must agree not to participate in a conception process (ie, active attempt to become pregnant or impregnation, sperm donation, in vitro fertilization) during the study and for 30 days after the last dose of study drug. Eligible subjects must meet all entry criteria prior to being randomized to receive study drug as outlined below. Any deviations from these criteria must be approved by the Sponsor prior to the subject being enrolled.

